2.2.4 LOW RISK PATIENTS DEFINED BY SURROGATES FOR FIBROSIS

BAVENO VI Criteria. The BAVENO VI conference provided guidelines for use of non- or minimally-invasive tests to determine likelihood of large esophageal varices in patients with CLD (3). The guidelines depend heavily upon LSM by TE. But, accuracy of TE for this purpose is questioned within the same document. To improve accuracy, the authors recommended two measurements on different days in fasting condition and also that invasive tests, such as liver biopsy or HVPG might be needed to confirm suspicion for cirrhosis or clinically significant portal hypertension (CSPH). HVPG was considered the gold standard for this assessment. They further concluded that the

diagnostic value of TE for CSPH remained to be ascertained across the spectrum of etiologies of CLD and that there was specific concern that TE would be less accurate in NAFLD and NASH.

Given the pitfalls of LSM alone, the BAVENO VI guidelines emphasized use of LSM with platelet count, specifically to use LSM <20 kPa and with a platelet count >150,000 μ L⁻¹, to select cases with a very low risk of having large esophageal varices, the varices needing treatment (3).

 Table 1: Selected Characteristics of Subjects in 10 Published Studies¹ using LSM plus Platelet Count for Likelihood of Large

 Esophageal Varices² Compared to the Subjects in the HALT-C Training Dataset

	Type of		E	9) tiology	%)					Crit	teria
Study	Study	N	EtOH	Viral	NAFLD	Male (%)	Age (yr)	CP A	t, LSM-EGD	LSM	Piti
Abraldes	Retro	379	14	70	6	NA	58	100	NA	25	15000
Ahmed	Retro	478	36	33	21	NA	54	NA	<1yr	20	1500
Chang	Retro	173	NA	55	NA	62	56	100	<1yr	20	1500
Ding	Retro	271	12	69	8	70	58	100	3.4 mo	25	1000
Maurice	Retro	310	13	62	14	67	58	89	<1yr	20	1500
Paternostro	Retro	92	30	47	NA	73	53	100	NA	20	1500
Puigvehi	Pro	368	0	100	0	63	57	100	NA	25	1000
Silva	Retro	112	7	83	NA	77	54	87	<1yr	20	1500
Thabut	Pro	649	0	100	0	73	56	100	NA	20	1500
Tosetti	Retro	146	0	100	0	NA	NA	100	NA	20	1500
HALT-C	Pro	217	0	100	0	76	50	100	2 wk, 6 mo, 18 mo	DSI	18.3

Abbreviations: Retro, retrospective study; Pro, prospective study; N, number of subjects; EtOH, alcohol-related liver disease; Viral, chronic viral hepatitis due to either HBV or HCV; NAFLD, non-alcoholic fatty liver disease; CP A, Child Pugh class A cirrhosis; LSM, liver stiffness measurement; EGD, esophagogastroduodenoscopy (endoscopy); t, LSM-EGD, time interval between performance of the LSM and performance of the EGD; Pltl, platelet count in μ L⁻¹. ¹From Marot, et al (6). All studies used LSM and platelet count with cutoffs similar to BAVENO VI criteria. The sample size of the HALT-C Training dataset was similar to the sample sizes of the individual studies and also similar in terms of etiology of CLD, male dominance, mean age, Child-Pugh class, and time interval between performance of the test and EGD. ²Large esophageal varices are varices of diameter 5 cm or more, or described as medium or large, or graded as 2 or higher. Large esophageal varices are considered high risk for variceal hemorrhage and its consequent morbidity and mortality. Large esophageal varices are varices that need treatment.

Published studies evaluating the BAVENO VI Criteria. Ten published studies, encompassing 2977 cases, using LSM and platelet count and criteria similar to BAVENO VI have focused on the need to identify the CLD patient at low likelihood of having large esophageal varices (3-11,28-30,38) (Table 1). In these reports, viral hepatitis was the most common etiology, followed by alcohol and NAFLD/NASH. Most were men with a mean age in the mid-50s. All had a diagnosis of cirrhosis and nearly all had Child-Pugh class A disease severity. These reports do not include subjects with either noncirrhotic fibrosis or Child-Pugh class B cirrhosis. The cases from the published literature have selected characteristics that are similar to the subjects in the HALT-C Training Dataset (Table 1).

Avoiding unnecessary EGD is a goal of screening. The percentage of unnecessary EGDs is defined by the number of cases with no or small varices that underwent EGD that would have avoided EGD by application of selection criteria. A meta-analysis of the 10 published studies suggested that application of BAVENO VI criteria might reduce screening or surveillance EGDs by 7% to 30% (6). Each of the 10 studies applied different combinations of cutoffs for platelet count (>100,000 μ L-1, >120,000 μ L⁻¹ or >150,000 μ L⁻¹) and LSM (<20 or <25 kPa). The individual study results were pooled, and the pooled estimates were sensitivity 93%, specificity 30%, negative predictive value (NPV) 97%, positive predictive value (PPV) 14%, negative likelihood ratio (NLR) 0.22, positive likelihood ratio (PLR) 1.33 (Table 2), and false negative rate (FNR) 3%. The analysis also revealed that 21 of 319 (6.5%) large varices needing treatment were missed (6). Another review further highlighted the relatively low rate of reduction in EGDs (20% overall) and unacceptably high FNR and rate of missed large varices or varices needing treatment (4).

Study	Prevalence	ТР	FN	FP	TN	Sens	Spec	PPV	NPV	FNR	PLR	NLR
Abraldes	0.15	54	3	238	84	0.95	0.26	0.18	0.97	0.03	1.28	0.20
Ahmed	0.11	49	3	318	108	0.94	0.25	0.13	0.97	0.03	1.26	0.23
Chang	0.08	11	3	128	31	0.79	0.19	0.08	0.91	0.09	0.98	1.10
Ding	0.10	26	0	138	107	1.00	0.44	0.16	1.00	0.00	1.78	0.00
Maurice	0.05	13	2	195	100	0.87	0.34	0.06	0.98	0.02	1.31	0.39
Paternostro	0.21	19	0	61	10	1.00	0.14	0.24	1.00	0.00	1.16	0.00
Puigvehi	0.15	45	10	174	139	0.82	0.44	0.21	0.93	0.07	1.47	0.41
Silva	0.18	20	0	80	12	1.00	0.13	0.20	1.00	0.00	1.15	0.00
Thabut	0.08	49	0	445	156	1.00	0.26	0.10	1.00	0.00	1.35	0.00
Tosetti	0.08	12	0	95	39	1.00	0.29	0.11	1.00	0.00	1.41	0.00
Pooled Totals	0.11	298	21	1872	786	0.93	0.30	0.14	0.97	0.03	1.33	0.22
Means of Studies	0.12	30	2	187	79	0.94	0.28	0.15	0.98	0.02	1.32	0.23
SD of Studies	0.05	17	3	119	52	0.08	0.11	0.06	0.03	0.03	0.21	0.35
HALT-C	0.10	21	1	89	106	0.95	0.54	0.19	0.99	0.01	2.09	0.08

Table 2: Diagnostic Performance of LSM + Platelet Count versus DSI for Likelihood of Large Esophageal Varices

Abbreviations: LSM: liver stiffness measurement by transient elastography; DSI, disease severity index from the HepQuant SHUNT test; TP, true positives; FN, false negatives; FP, false positives; TN, true negatives; Sens, sensitivity; Spec, specificity; PPV, positive predictive value; NPV, negative predictive value; FNR, false negative rate; PLR, positive likelihood ratio; NLR, negative likelihood ratio; HALT-C, the NIH-sponsored Hepatitis C Antiviral Treatment to Prevent Cirrhosis Trial.

NLR is a statistical endpoint that encompasses both sensitivity and specificity in its calculation and is not dependent upon prevalence. In these 10 published studies NLR ranged from 0 to 1.10 – a wide variation due to lack of prespecified study design or criteria and a range for sensitivity that varied from 79% to 100%.

The lower the NLR the greater the strength of "Rule Out" of likelihood of large esophageal varices. The NLR of 0.09 using DSI 18.3 from our HALT-C Training Dataset is favorable, compared to either the pooled results or mean (±SD) of individual studies using LSM plus platelet count displayed in **Table 2**.

In the ANTICIPATE study, 30% of EGDs could have been avoided but 5% of varices needing treatment would have been undetected (29). Most recently, the ANTICIPATE cohort was combined with two other single center cohorts (total N=925) (30). LSM <25 and platelet count >110,000 μ L⁻¹ were evaluated for exclusion of EGD and suggested that 40% of EGDs might have been avoided, but 6.5% (6/92) of the large varices or VNT were missed. A further modification, the addition of MELD=6 to platelets >100,000 μ L⁻¹ and LSM <25 kPa, would have spared 46% of EGDs, but 7.6% (7/92) of the large varices or VNT were missed.

Limitations of Existing Data. The studies using LSM and platelets were limited by referral and selection bias, retrospective analyses, differences in criteria for EGD, and use of different cutoffs for LSM and platelet count. For example, one of the largest studies screened over 12,000 LSM measurements to select 310 patients and the time between the screening tests and EGD was up to 12 months (28). In the meta-analysis only 15 of 419 references were selected and there were nearly 3 times as many cases above cutoffs compared to the cases below cutoffs (6). The 95% confidence intervals for NLR from these studies were extremely wide. In the study of Expanded BAVENO VI Criteria, three cohorts with very different results were combined – the percentage of EGDs spared were 32%, 41%, and 52% (30). In addition, the prevalence of large esophageal varices or varices needing treatment varied greatly between publications. For example, the prevalence of large varices or VNT ranged from 0% to 21% in the 10 studies with data for large varices in Marot's meta-analysis (6). And, it is not clear in all studies that the tests used for "selection" of EGD were actually performed prior to EGD. Accordingly, a prospective study with prespecified endpoints and statistical plan, as proposed herein for DSI, is critically needed.

The HepQuant SHUNT Approach. DSI from the HepQuant SHUNT Test has shown promise as a potential tool to aid in the decision to avoid or perform EGD for large esophageal varices. In our analyses of the HALT-C Training dataset,

we found that the DSI cutoff 18.3 demonstrated a negative likelihood ratio (NLR) 0.09 for large esophageal varices (**Table 2**) – a result that would have avoided 49% of EGDs. If the DSI cutoff \leq 18.3 were applied to the cases comprising the published studies of transient elastography plus platelet count described above, there would have been a reduction in EGDs of 52%. These results compare favorably with the reported 7 to 30% reduction (6), or 20% overall reduction (4), in EGDs for LSM plus platelet count. In addition, the false negative rate is very low with DSI \leq 18.3 – NPV >99%, FNR <1% with only 1 of 22 large varices missed. The potentially greater reduction in unneeded surveillance EGDs (52% vs 20%) and low number of false negatives favor the use of the DSI. A reduction in number of unnecessary screening or surveillance EGDs by approximately 50% is highly clinically relevant.

There may be additional advantages of the HepQuant SHUNT test. The test is done once, while TE is recommended to be done at least twice on two separate days. Both tests require fasting. The NLR of 0.09 for DSI \leq 18.3, compared to published NLRs, suggests that the DSI cutoff may be more accurate in negative likelihood of large esophageal varices compared with the current practice using LSM with or without platelet count.

High Risk Patients defined by Cirrhosis or Advanced CLD

In the ANTICIPATE Study (29) liver stiffness, platelet count, and spleen diameter were evaluated in 518 patients with CLD from five centers in Europe and Canada. Liver stiffness measurement [LSM] by transient elastography [TE], platelet count, and spleen diameter (with calculation of liver stiffness to spleen/platelet score [LSPS] score and platelet-spleen ratio [PSR]) were compared in their ability to predict risk of large esophageal varices ("varices needing treatment, VNT"). The AUROCs were 0.67 for TE alone, 0.73 for TE plus platelet count, 0.74 for PSR, and 0.79 for LSPS.

Furthermore, a diagnosis of cirrhosis, whether by biopsy or noninvasive means, does not provide an unequivocal link to varices or need for endoscopy. Many patients with cirrhosis lack clinically significant portal hypertension and do not have varices. Care providers don't necessarily link cirrhosis, per se, to need for endoscopy. The latter is exemplified by a study of 4230 veterans with HCV cirrhosis with median followup of 6.1 years. Only 33.8% of patients meeting AASLD or Bueno VI guidelines had an EGD performed for variceal screening (77). Diagnosis of cirrhosis fails to trigger care providers to refer patients for endoscopic variceal screening.

The HepQuant SHUNT Approach. The HALT-C Training Dataset defined an AUROC 0.82 for DSI in likelihood of Large Esophageal Varices. This compares favorably with AUROCs measured in the Anticipate Study – ranging from 0.67 for TE alone, to 0.79 for LSPS. The performance of HepQuant SHUNT and DSI for likelihood of Large Esophageal Varices is due to the fact that the HepQuant SHUNT test directly measures portal-systemic shunting, linking it directly to variceal pathophysiology. As such, a HepQuant SHUNT test result may provide a more direct link to varices resulting in an appropriate referral for endoscopy.

2.2.5 HIGH RISK PATIENTS DEFINED BY MEASUREMENT OF THE PORTAL CIRCULATION

HVPG. Portal hypertension, the cause of esophageal varices, can be indirectly measured by percutaneous transjugular catheterization of the hepatic venous system to quantify the hepatic venous pressure gradient (HVPG) (39,78-82). HVPG correlates well with the direct measurement of portal pressure. Clinically significant portal hypertension is defined by HVPG \ge 10 mmHg (some studies suggest \ge 12 mmHg) and correlates well with risk for varices and variceal hemorrhage. In the US, most HVPG studies are performed in specialized radiology departments. Measurement of HVPG is technically challenging, time consuming, and performed in specialized units; the procedure is invasive, poorly tolerated, risky, and not embraced by patients. Also, the reproducibility of HVPG is questionable, especially if performed only sporadically in less experienced units. Even in experienced centers, HVPG reproducibility is of concern. For example, in a study of patients with HCV and underlying portal hypertension, the mean (±SD, CV%) difference in repeated measurements of HVPG was 0.5 ± 2.52 mmHg (82).

The HepQuant SHUNT Approach. HepQuant SHUNT measures portal-systemic shunting and could be an alternative to HVPG to define groups with or without risk for large esophageal varices. The HepQuant SHUNT Test

satisfies the unmet medical need for a simple-to-administer, well-tolerated, relatively inexpensive, safe, and minimally-invasive test. The overall hypothesis for the SHUNT-V study is that the HepQuant SHUNT Liver Diagnostic Test can measure the liver and portal circulation in patients with CLD and identify those patients who are or are not likely to have large esophageal varices.

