2.2.6 FULFILLING AN UNMET NEED

[figure not shown]
The results from the above studies demonstrate the need for new innovative, non- or minimally-invasive tests to replace the invasive tests and to improve the accuracy of current non- or minimally-invasive tests. The data suggest that the HepQuant SHUNT Test can potentially fulfill this unmet need. Our proposed validation study is a prospective multi-center study of sufficient power to define the cutoff for DSI for both ruling in and ruling out large esophageal varices.

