4.1.3 ANALYSES

The relationship of DSI to the primary endoscopic endpoint of large esophageal varices will be analyzed by univariate and multivariate logistic regression analyses, ROC curve analysis, and linear and nonlinear regression and correlation coefficients. The diagnostic performance of DSI cutoff 18.3 will be defined in terms of sensitivity, specificity, PPV, NPV, NLR, FNR, and miss rate⁴. For the primary efficacy endpoint, validation of DSI \leq 18.3 as a cutoff for negative likelihood of large esophageal varices will require two that two criteria are satisfied: (a) confidence interval with an upper limit that rules out NLR > .52 and (b) the observed sensitivity > 0.85.

There are no planned stratifications or sub-studies.

A single interim analysis is planned after the trial data set has compete DSI and EGD measurements on approximately 250 participants. The objective of the interim analysis will be to determine whether DSI \leq 18.3 has sufficient sensitivity and specificity to rule out NLR for large varices > 0.52, and that the observed sensitivity demonstrates an acceptable number of false negative results. The interim decision criteria have been chosen using standard group sequential designs as described in Section 9.5.1. The interim analysis will be performed by an independent statistician. The results of the interim analysis will be reviewed and interpreted by the biostatistician, who will determine if the trial should continue to full enrollment or if it can be stopped for either efficacy or futility.

Minimizing Bias: See Section 6.6.

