4.2 Scientific Rationale for Study Design

This is a USA multi-center, open-label, single-arm study with a point-in-time analysis to validate the DSI cutoff ≤18.3 from the HepQuant SHUNT Test for negative likelihood of large esophageal varices.

The rationale for this study is based upon our analysis of patients with chronic hepatitis C who were enrolled in the HALT-C Trial **(HALT-C Training dataset)**. We examined the relationship of DSI to likelihood of varices in this Trial and found that DSI \leq 18.3, had NPV >99%, FNR <1%, and NLR 0.09; indicating that DSI \leq 18.3 could potentially be a cutoff to "Rule Out" large esophageal varices.

The **primary objective** is to validate the cutoff of DSI \leq 18.3 to "Rule Out" large esophageal varices using a properly powered prospective study of subjects with CLD of various etiologies and spectrum of severity of disease (CLD Validation dataset).

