4.2.3 DSI 18.3 FROM THE HALT-C TRAINING DATASET IS A CLINICALLY MEANINGFUL CUTOFF

As stated at the introduction to this application, the primary objective of this study is to validate DSI \leq 18.3 as a cutoff for "Rule Out" of large esophageal varices. In HALT-C, DSI \leq 18.3 had NPV >99%, NLR 0.0926, and FNR 1%. A person with DSI \leq 18.3 may be able to avoid EGD; reducing healthcare costs, improving clinical management, and enhancing the person's experience.

Patients with large esophageal varices (>5 mm diameter) are at immediate risk for variceal hemorrhage and need urgent treatment. The HALT-C Training dataset indicated that likelihood for large esophageal varices or varices of any size is proportional to DSI, as DSI increases likelihood for both large varices and varices of any size increases. DSI >18.3 had sensitivity 95% and PLR 2.09; "Ruling In" large esophageal varices. A patient with DSI >18.3 may be a candidate for EGD. Performing EGD and initiating treatment due to early detection of large esophageal varices can also reduce health care costs and improve patient management by preventing subsequent variceal hemorrhage and the associated morbidity and mortality.

[figure not shown]

Figure 9: Comparison of DSI with Liver Biopsy

Both fibrosis stage by METAVIR and the range of DSI by HepQuant SHUNT test correlate with risk for any but especially large varices. The DSI cutoff 18.3 has improved diagnostic performance for large varices, compared to histologic diagnosis of cirrhosis.

The cutoff of DSI 18.3 corresponding to sensitivity of 95% (CI 93% to 98%) for large varices compares favorably with the gold standard of biopsy-diagnosed-cirrhosis which has a sensitivity of only 77% (**Figure 9**) and, as noted previously, the current noninvasive practice using LSM plus platelet count. Therefore, fewer cases of dangerous large varices are missed when using DSI.

DSI cutoff of 18.3 also identified the patients with any size varices (52 small and 22 large) with 69% sensitivity (CI 57% to 79%), specificity 58%, PPV of 46%, and NPV of 78%.

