9.2 Sample Size Determination

9.2.1 PRIMARY EFFICACY ENDPOINT: SAMPLE SIZE AND POWER

Based on NLR

The trial sample size was evaluated and selected to assure adequate statistical power that the upper limit of the 95% CI for NLR will be smaller than 0.52. For design purposes we evaluate power and sample size using the variance from Table 9 equation E under the hypothesis that NLR = 0.20 with sensitivity = 0.90, specificity = 0.50, and 20% prevalence of large varices (i.e., 80 subjects with large varices = 0.2x400). A sample size of 400 participants (80 with large varices, 320 without) was selected to provide adequate power based on the following power characteristics:

		Power	for variou	ıs sample	sizes
NLR	FNR	380	400	420	440
0.20	0.048	0.78	0.80	0.82	0.84
0.19	0.045	0.82	0.84	0.86	0.87
0.18	0.043	0.86	0.88	0.89	0.91
0.17	0.041	0.89	0.91	0.92	0.93
0.16	0.038	0.92	0.93	0.94	0.95
0.15	0.036	0.95	0.96	0.96	0.97

Table 10: Initial Power Analysis for Selection of N-400

In this analysis 400 subjects provide over 80% probability/power of rejecting the rule-out hypothesis of NLR > 0.52 when the true NLR is smaller than 0.20. From Table 9 equation D, NLR = 0.2 corresponds to FNR = 0.048; thus, the trial has more than 80% power for FNR smaller than 5%. With 400 subjects, the upper limit of the 95% confidence will exclude NLR > 0.52 if the NLR in the trial is smaller than 0.27; that is, the threshold (critical value) for rejecting the NLR null hypothesis is NLR≤0.27 (corresponding to FNR smaller than 6.5%). This evaluation is based on the large-sample variance of equation E and is adequate for selecting the total sample size for the trial. A complete power evaluation of trial power with and without an interim analysis requires a simulation study as described in section 9.5.1.

Based on Predictive Value of a Negative Test (NPV)

NPV is the probability that a subject with DSI \leq 18.3 does not have varices, and the false negative rate is defined from NPV according to equation D in **Table 9**. The goal is to ensure that *NPV is suitably large and FNR* is suitably small. NLR can also be written in terms of NPV. From equation D, *NLR* <0.27 corresponds to FNR <6.5% and a NPV over 0.937. Similarly, the critical value rules out NLR > 0.52, which corresponds to NPV > 0.885 (FNR < 11.5%). The study sample size gives 80% power under the hypothesis that *NLR* = 0.2, which corresponds to FNR < 5%.

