9.4.2 ANALYSIS OF THE PRIMARY EFFICACY ENDPOINT(S)

[figure not shown]
Primary efficacy endpoint (DSI \leq18.3 "Rules Out" Large Esophageal Varices): The independent variable is DSI and the dependent variable is the presence/absence of large esophageal varices diagnosed by EGD within 42 days of the HepQuant SHUNT test. The sample size evaluation of section 9.2.1 is based on the large-sample variance of **Table 9** equation E. This equation cannot be used for data analysis if sensitivity is close to 1.0 (Marril, et al [118]). The following methods will be used to evaluate whether the trial results satisfy the performance goals for NLR and sensitivity:

Rule out NLR > 0.52: This objective will be satisfied if the upper limit of the confidence interval for NLR is smaller than 0.52. The score-based confidence interval that is derived by inverting the score test (see Marril, et al. [118]) will be used to calculate the NLR confidence interval. The confidence level will be chosen to assure an overall one-sided type-I error rate of 0.025 as described in section 9.5.1.

Sensitivity >= 0.85: This objective will be satisfied if the observed sensitivity is larger than 0.85. The corresponding 95% confidence interval will also be reported and will be calculated using the exact binomial distribution.

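### Section 2.2.6 claims power to define a DSI cutoff for ruling in large varices, but the plan specifies and powers rule-out only

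*Combined protocol and SAP*

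**What the plan says.** Three background or rationale statements point in the rule-in direction:

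- Section 2.2.5, overall hypothesis: the test can "identify those patients who are or are not likely to have large esophageal varices".
- Section 2.2.6: the study is "of sufficient power to define the cutoff for DSI for both ruling in and ruling out large esophageal varices".
- Section 4.2.3: "DSI >18.3 had sensitivity 95% and PLR 2.09" in HALT-C, followed by a rule-in label for that result.

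The operative sections are about ruling out:

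- Section 4.2 describes validation of the cutoff "from the HepQuant SHUNT Test for negative likelihood of large esophageal varices".
- Section 4.1.3 requires "a) confidence interval with an upper limit that rules out NLR > .52 and (b) the observed sensitivity > 0.85" for success.
- Section 9.4.2 controls error for the NLR criterion: "The confidence level will be chosen to assure an overall one-sided type-I error rate of 0.025".
- Section 9.2.1 sizes the trial so that the "upper limit of the 95% CI for NLR will be smaller than 0.52".
- Section 9.5.1 bases the interim efficacy and futility rules on NLR and sensitivity.

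The secondary endpoint (Sections 3, 9.1.2 and 9.4.3) is a logistic regression of large varices on DSI, with the hypothesis that the slope exceeds zero and a comparison of observed with expected probabilities by DSI category. Section 9.2.2 asserts adequate power for secondary and exploratory endpoints without a calculation. The exploratory search for an optimal DSI (Sections 4.3.2 and 9.6.2) looks for the best rule-out value.

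**The concern.** Section 2.2.6 attributes to the design a property that Section 9 does not provide. To be powered to define a rule-in cutoff, a study needs a candidate cutoff or a rule for choosing one, a performance bar, an error rate and a calculation. None is given for ruling in.

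The risk lies in interpretation. If the trial meets its NLR and sensitivity criteria, Sections 2.2.6 and 4.2.3 could be cited as showing that DSI >18.3, or some higher value picked from the data, has been validated for ruling in. Section 9.6.2 plans a table of performance over the DSI range that may go into a package insert, so the status of those figures matters.

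**Working it through.** **Inputs.** N=400, with 80 subjects with large varices and 320 without, sensitivity 0.90, specificity 0.50, prevalence 20% (Section 9.2.1). HALT-C counts: TP 21, FN 1, FP 89, TN 106 (Table 2). Specificity 0.28, stated to be acceptable provided NLR >0.52 is excluded (Section 9.4.2). Variance equations E and F (Table 9). Pairing specificity 0.28 with sensitivity 0.95 is my choice; 95% is the HALT-C sensitivity.

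**1. The plan's own power figure is a rule-out figure.** Equation E: 0.90/(0.10×80) + 0.50/(0.50×320) = 0.1125 + 0.0031 = 0.1156, SE 0.340.

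- Power = Φ[(ln 0.52 − ln 0.20)/0.340 − 1.96] = Φ(0.85) = 0.802, against 0.80 stated.
- Critical value = 0.52 × exp(−1.96×0.340) = 0.267, against 0.27 stated.

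Table 10 is therefore a calculation on NLR. Tables 12 and 13 use NLR and sensitivity. PLR and PPV enter none of them.

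**2. What a result above 18.3 would mean.** PLR = sensitivity/(1 − specificity). At 20% prevalence the prior odds are 0.25, so PPV = 0.25×PLR/(1 + 0.25×PLR).

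| Setting | Sens / spec | PLR | PPV at 20% prevalence |
|---|---|---|---|
| Design values | 0.90 / 0.50 | 1.80 | 0.45/1.45 = 31% |
| HALT-C counts | (21/22) / (106/195) | 2.09 | 0.523/1.523 = 34% |
| Specificity at the stated floor | 0.95 / 0.28 | 1.32 | 0.330/1.330 = 25% |

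The HALT-C PPV of 21/110 = 19% belongs to a prevalence of 22/217 = 10% and should not be set against a 20% prior.

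**3. The third row meets the success rule.** NLR = 0.05/0.28 = 0.179. Equation E: 0.95/(0.05×80) + 0.72/(0.28×320) = 0.2375 + 0.0080 = 0.2455, SE 0.4955.

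- Upper 95% limit = 0.179 × exp(1.96×0.4955) = 0.47.
- At the 96.07% level set for the full-sample analysis in Section 9.5.1 (z = 2.061) it is 0.50.
- The plan will use a score interval. Inverting the score test for the ratio of 4/80 to 90/320 gives upper limits of about 0.44 (95%) and 0.46 (96.07%).

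All are below 0.52 and sensitivity exceeds 0.85, so the trial succeeds although a positive test moves the probability only from 20% to 25%.

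**4. Rule-in power depends on a bar that is not stated.** Equation F at the design values: 0.10/(0.90×80) + 0.50/(0.50×320) = 0.00451, SE 0.0672, so the 95% CI for PLR is 1.80 × exp(±0.1317) = 1.58 to 2.05. Taking assumed bars, and power = Φ[(ln PLR − ln bar)/SE − 1.96]:

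- Bar 1.5: 77% at design values, 99.9% at HALT-C values.
- Bar 2: 0.02% and 10%.
- Bar 3: essentially 0% for both.

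The bars are illustrations only. They show that sufficient power for ruling in has no meaning until a bar is named.

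**The case against.** The strongest reply is that the patients who are likely to have large varices are not ignored. The secondary objective models probability against DSI, states a directional hypothesis and checks calibration by DSI category. In HALT-C the slope was 0.1947 with SE 0.0403, a Wald z of 4.8. That stands: the Section 2.2.5 hypothesis is covered by the primary and secondary objectives together, and narrowing it to rule-out would contradict the secondary objective. A positive slope is still association; it defines no cutoff.

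Reporting is largely in place. Section 9.4.3 already gives PPV and PLR with 95% CIs at 18.3, and Section 4.3.2 foresees CIs over the DSI range, though its list for large varices omits PLR. Section 9.6.2 lists PLR for the table but mentions no intervals. What is missing is a statement that these figures are descriptive.

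Section 2.3.1 says a false positive has no clinical consequence, because patients are already scheduled for EGD. That explains why no rule-in test was planned. It does not support claiming power for one.

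Section 2.2.6 speaks of a single cutoff, which may mean 18.3, where PLR would be estimated quite precisely (1.58 to 2.05 at the design values). Precision is not a rule-in criterion. Section 4.3.2 also mentions the Youden index, but that balances sensitivity and specificity and is not a rule-in criterion either.

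**Conclusion.** The claim of power in Section 2.2.6 is unsupported, and the rule-in label in Section 4.2.3 rests on training data with no validation criterion behind it. Primary success is compatible with a PPV of 25% to 34% above 18.3 at 20% prevalence. The range assumes the planned prevalence and the three sensitivity and specificity pairs shown.

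A reader might infer more than this, and the documents do not support it:

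- *That DSI >18.3 cannot rule in.* The plan sets no PLR or PPV bar, so this would be a judgement. The point is that rule-in value is not tested.
- *That no analysis addresses patients likely to have large varices.* The secondary graded-probability analysis does.
- *That a high cutoff such as DSI 33.2, where HALT-C probability reached 50%, would be too imprecise.* The plan proposes no such cutoff, and scaling counts from a compensated hepatitis C cohort with 10% prevalence to this population would be an assumption.
- *That the primary analysis is compromised.* Its hypothesis, error rate, sample size and interim rules are unaffected.

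This is an inconsistency in stated scope, worth correcting because it limits what may be concluded from a positive trial.

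**What to change.** - Section 2.2.6: replace the power claim with a statement that the study is powered to validate the prespecified rule-out cutoff DSI ≤18.3, and that no rule-in cutoff is defined, powered or will be claimed.
- Section 4.2.3: remove the rule-in label and leave PLR 2.09 as a training-data result.
- Section 2.2.5: keep the hypothesis, adding that its affirmative half is addressed only by the secondary graded-probability analysis.
- Sections 9.4.3 and 9.6.2: state that PPV and PLR for DSI above 18.3 are descriptive, and that the table over the DSI range will carry 95% CIs, PLR included.

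If a rule-in claim is wanted, the alternative is to prespecify a cutoff with its own PLR or PPV criterion, error control and power.

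The wording changes make the stated scope less favourable. They cost nothing in sample size or data and leave the primary analysis as it is.
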